 - a. Patients will receive cyclosporine A (CSA) therapy beginning on Day -3 maintaining a trough level between 200 and 400 ng/mL by HPLC analysis (250 and 500 ng/ml by immunoassay). For adults the initial dose will be 2.5 mg/kg IV over 1 hour every 12 hours. For children < 40 kg the initial dose will be 2.5 mg/kg IV over 1 hour every 8 hours.
 - b. Dose adjustments will be made on the basis of toxicity and low CSA levels with a trough level of <200 mg/L (HPLC). Once the patient can tolerate oral medications, CSA will be converted to an oral form. CSA dosing will be monitored and altered as clinically appropriate.
 - c. Patients will receive CSA until Day +100. If there is no evidence of GVHD, the dose will then be tapered 10% per week starting on Day +101 and discontinued no sooner than 6 months post transplant.
2. Mycophenolate mofetil (MMF)
 - a. All patients will receive MMF at the dose of 15 mg/kg IV (based on adjusted weight) every 8 hours with a maximum of 1 gram/dose starting 4-6 hours after infusion of UCBT on Day 0. If actual body weight is < ideal weight, calculation based on actual weight is allowed. Rounding of the dose to the nearest 250 mg capsule size is also allowed. Once the patient can tolerate oral medications, MMF may be converted to an oral form.
 - b. MMF will be given every 8 hrs daily until day 40 post transplant and then in the absence of GVHD, tapered by 12%/week with MMF discontinued

after day + 96. If GVHD has been diagnosed, continued treatment and eligibility for acute GVHD protocols is at the attending physician's discretion. It is recommended in this setting that MMF be tapered after initiation of therapy for acute GVHD has been started and there is documented response. This is at the attending physician's discretion.

- c. MMF dosing to be monitored and altered as clinically appropriate.
- d. Markedly low (<40%) donor T cell chimerism after UCBT may indicate impending graft rejection. MMF should be continued at full dose or, if MMF taper has been initiated, reinstitution of full dose MMF should occur. If MMF has been discontinued, MMF should be reinitiated at full dose.

C. Umbilical Cord Blood Transplant (UCBT)

- 1. Procedures for requesting, receiving and characterizing the cord blood unit for infusion will be according to institutional protocol. Procedures for transplantation at outside centers will be reviewed and approved by the PI.

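### Section 8.B.1 states the cyclosporine target trough in ng/mL but the low level prompting dose adjustment in mg/L, so the two items differ by a factor of 1000 as written

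*Combined protocol and SAP*

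**What the plan says.** Section 8.B puts every patient on two-drug GVHD prophylaxis, and Section 8.B.1 covers cyclosporine.

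- **Item a** starts the drug on day -3, "maintaining a trough level between 200 and 400 ng/mL by HPLC analysis", and gives a parallel range of "250 and 500 ng/ml by immunoassay".
- **Item b** turns to changes of dose: "Dose adjustments will be made on the basis of toxicity and low CSA levels". It then puts a number on low, also for HPLC: "trough level of <200 mg/L (HPLC"). It closes by saying that dosing is monitored and changed as clinically appropriate.

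No other section or appendix states a cyclosporine concentration, in any unit.

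**The concern.** The two items describe the same drug, the same trough sample and the same assay, but in units that differ by a factor of 1000. Taken at face value, a trough inside the item a target is also a low trough under item b, so the two instructions cannot both be followed literally.

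This is working text. Item b holds the only number in Section 8.B.1 that is tied to a change of dose, and the instruction applies to all patients. The protocol also provides for transplants at outside centers (Section 8.C) and for collaborating sites (Section 12.C), whose staff work from this wording. Section 10.A.3 lists nephrotoxicity and seizures among the drug's toxicities, so a threshold that could be misread deserves correction even if most readers would see past it.

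**Working it through.** **Inputs, all from Section 8.B.1**

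| Quantity | Item | Value as written |
|---|---|---|
| Target trough, HPLC | a | 200 to 400 ng/mL |
| Target trough, immunoassay | a | 250 to 500 ng/mL |
| Low level prompting adjustment, HPLC | b | below 200 mg/L |

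**Step 1: conversion factor.** 1 mg = 1,000,000 ng and 1 L = 1000 mL, so 1 mg/L = 1,000,000 / 1000 = 1000 ng/mL.

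**Step 2: item b in the unit of item a.** 200 mg/L × 1000 = 200,000 ng/mL.

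**Step 3: compare with item a.**

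- Lower HPLC bound: 200,000 / 200 = 1000.
- Upper HPLC bound: 200,000 / 400 = 500.
- Upper immunoassay bound: 200,000 / 500 = 400. This is for scale only, because item b names HPLC alone.

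**Step 4: the reverse conversion.** The lower bound in item a, 200 ng/mL, is 200 / 1000 = 0.2 mg/L, or 200 micrograms per litre. So if item b were expressed in micrograms per litre, or in ng/mL, its figure of 200 would coincide exactly with the lower bound in item a. That coincidence points to a slip in the unit rather than to two different clinical rules. It does not establish which wording the sponsor intended.

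**Step 5: does anything depend on it?** The figure enters no calculation. Section 14 uses graft failure and day-200 non-relapse mortality, and neither the 10% and 25% benchmarks nor the stopping boundaries involve a drug level.

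**The case against.** **It may not be in the source document.** The discrepancy rests on one character, since a micro sign read as the letter m would produce exactly this text. Conversion of a document to text can do that, and the micro sign appears in more than one form elsewhere. This stands as a possibility. Against it, the sign does come through in the neutrophil criteria of Section 3.A and in Section 8.G, and nothing in the documents shows a loss at this spot. Looking at the source file settles the matter.

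**Any clinician would read it correctly.** Largely granted. Item a gives the range, with an upper bound, immediately beforehand. Calling a level low makes sense only relative to that range. Item b also names toxicity as a separate ground for adjustment and ends with clinical discretion. These features limit the practical risk, but they do not make the two items consistent.

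**A stronger reading is tempting.** A reader might infer that patients at or far above target would in practice be managed as under-dosed, and that the resulting toxicity, GVHD or graft loss would feed both primary endpoints. The documents do not support this. The first part requires ignoring item a's upper bound and item b's other provisions. For the second, the protocol gives no data relating cyclosporine trough to graft failure or day-200 non-relapse mortality. Its stated response to low donor T-cell chimerism, in Section 8.B.2, concerns MMF.

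**Item b has no immunoassay figure.** A reader might also see this as part of the same defect. It is a separate drafting choice, because item a already gives the immunoassay range and the contradiction concerns the HPLC unit only.

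**Conclusion.** The point holds as an internal contradiction of unit. On the text as it stands, the low level in item b is 200,000 ng/mL, 1000 times the lower bound of the HPLC target in item a, and nothing elsewhere reconciles the two. The likeliest explanation is a unit slip, given the matching number, sample and assay.

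The consequence is modest. The intended frame is visible in item a, and item b leaves room for toxicity and clinical judgement. Sample size, error rates, stopping boundaries and the analysis of the primary endpoints are unaffected, and no harm to patients is inferred. It is still worth correcting, because it is an operative threshold for a drug that every patient receives and the correction costs almost nothing.

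The conclusion assumes that the unit printed in the source file is the one in the text. If the source shows a micro sign there, the contradiction disappears.

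**What to change.** Check the unit in Section 8.B.1 item b against the source file. If it reads mg/L there, reconcile items a and b so that both express the HPLC trough in the same unit, with the sponsor confirming the intended figure. This review does not say which item is right and proposes no level or dose.

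The cost is one line in the next amendment. No design element, data item or analysis changes.

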While a TREO based UCBT regimen holds appeal, two significant concerns specific to the UCBT setting include probable delayed engraftment and the possibility of graft failure. In Minnesota's initial effort at RIC UCBT, it performed 21 transplants following conditioning with BU 8 mg/kg, FLU 200 mg/m², and 200 cGy TBI. This regimen was associated with neutrophil engraftment at 26 days (12-30) and this delayed neutrophil engraftment resulted in Minnesota switching to the FLU/CY/TBI +/- ATG regimen that is the basis for FHCRC protocol 2012 [25]. The switch to a FLU/CY/TBI regimen in Minnesota resulted in initial autologous hematopoietic recovery, and a decrease in time to neutrophil engraftment to a median of 12 days (range, 0-32). Similarly, in our experience, median time to engraftment on protocol 2012 is 11 days (6-49) compared to 25 days (14-44) on the myeloablative UCBT FHCRC protocol 2010. Based on experience in the traditional donor setting with TREO based regimens [26], as well as Minnesota's experience with an intermediate dose BU based regimen, we expect that a TREO based UCBT regimen will result in prolonged neutropenia. Given the older age and higher comorbidities of patients generally considered for RIC, this prolonged neutropenia is a significant concern. For patients at high-risk for relapse, however, we believe the potential benefit of the increased anti-leukemic effect outweighs the risks.

Our concern about graft failure in the UCBT setting stems from other centers' experience with BU/FLU based regimens. Minnesota experienced 4 graft failures in their first 21 RIC patients receiving BU/FLU (albeit in patients at risk for graft failure by virtue of less treatment before transplant) [25]. Duke has recently reported very high graft failures (6/10 graft failures) following IV BU 520 mg/m² (mean AUC 4181 umol-min), FLU 160 mg/m² [27]. Spain, however, has reported good engraftment using a thiotepa 15mg/kg, IV BU 9.6 mg/kg, FLU 150 mg/m², ATG 8 mg/kg preparative regimen [28]. Patients undergoing an RIC regimen with cord blood as the donor source are at an increased risk of graft failure. Though TREO is likely more immunosuppressive than BU and may promote enhanced engraftment as compared to BU, we believe that a TREO/FLU based regimen may require additional immunosuppressive therapy to promote engraftment. We therefore propose a TREO/FLU regimen using TREO 42 g/m² and

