FLU 150 mg/m² similar to that established in the FHCRC/OHSU Phase 1 study in the traditional donor setting with the addition of a single dose of 200 cGy TBI. Dose escalation rules are established to first increase FLU to 200 mg/m² and then increase TBI to 300, 400, and 450 cGy TBI in the event of excessive graft failures.

Previous experience with RIC UCBT suggests that patients who have had limited prior therapy are at particularly greater risk for graft failure. For the purposes of determining acceptable engraftment rates following TREO/FLU/TBI, patients will be classified as low risk for graft failure (Arm 1) or high risk for graft failure (Arm 2) as follows. For each arm, a true probability of graft failure of 5% (or less) will be accepted without dose escalation.

- Arm 1: Low-risk patients include those who have received ≥ 2 cycles of multiagent chemotherapy and at least one cycle of therapy within the 3 months previous to UCBT.
- Arm 2: High-risk patients include those who have received no multiagent chemotherapy or immune suppressive chemotherapy in the 3 months prior to transplant or have received only a single induction therapy.

We believe that a TREO/FLU based conditioning regimen may improve outcomes for acute leukemia and MDS UCBT patients unable to tolerate high-dose myeloablative therapy but at high risk for relapse. In addition to possibly improving outcomes for those RIC patients at high-risk for relapse, a TREO regimen would provide a higher intensity chemotherapeutic treatment option for patients ineligible for high dose radiation and therefore ineligible for FHCRC protocol 2010. Experience with the regimen in this setting may lead to its extension to a broader group of cord patients.

3. Objectives

A. Primary Objective:

The primary objective of this study is to show that TREO/FLU/TBI as a sufficient conditioning regimen reduces the probability of graft failure as compared to an historical benchmark and that the risk of day -200 NRM is not higher than a relevant historical benchmark. Patients will be divided into two arms based on risk of graft failure as described above.

Primary endpoints are as listed below:

1. Graft failure/rejection and secondary graft failure. Patients will be considered primary graft failure/rejections provided they meet any criteria listed below:
 - i. Absence of 3 consecutive days with neutrophils $\geq 500/\mu\text{l}$ combined with host CD3 peripheral blood chimerism $\geq 50\%$ at day 42

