1. Any cord blood units with $<1.5 \times 10^7$ total nucleated cells per kilogram recipient weight.

2. Any cord blood units without full maternal testing and negative results for hepatitis B, C, HIV, and HTLV-1 viruses. Any additional available virology results on the unit itself will be reviewed but are not mandated, complete or always available. Cord blood units are presumed to be CMV negative regardless of serologic testing due to passive transmission of maternal CMV antibodies.

6. Evaluation and Counseling of Patient

The patient and donor units will be completely evaluated per standard practice. The protocol will be discussed thoroughly with patient and caregivers, and all known risks to the patient will be described. The procedure and alternative forms of therapy will be presented as objectively as possible and the risks and hazards of the procedure explained to the patient or, in the case of minors, to the patient's responsible family members. Informed consent from the patient will be obtained using a consent document approved by the Institutional Review Board (IRB) of the Fred Hutchinson Cancer Research Center.

7. Protocol Registration

FHCRC patients: Eligible patients will be identified by the Clinical Coordinators Office. Patients will be registered with the Registration Office [contact]) between 8:30 am and 4:00 p.m. Pacific time, Monday through Friday. After hours, the Registration office can be reached by paging [contact].

8. Plan of Treatment

A. Conditioning Regimen

The study has two arms, determined by risk for graft failure as outlined below:

Arm 1: Low-risk patients include patients who have received ≥ 2 cycles of multiagent chemotherapy and at least one cycle of therapy within the 3 months previous to UCBT.

Arm 2: High-risk patients include patients who have received no multiagent chemotherapy or immune suppressive chemotherapy in the 3 months prior to transplant or have received only a single induction therapy.

Conditioning regimen for both arms will be the same initially. As outlined in the Statistical Considerations (Section 14), dose escalations will occur in either arm if sufficient evidence exists to suggest that the true probability of graft failure exceeds 5%. Stepwise dose escalation if graft failures persist will be to first increase fludarabine to 200 mg/m^2 (administered at 40 mg/m^2 daily days -6 to -2), then to escalate TBI to 300 cGy, then to 400 cGy, then to 450 cGy.

| | |
|--------|---|

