| Day -6 | Fludarabine 30 mg/m ² IV over 1 hour* Treasulfan 14 g/m ² IV over 2 hours |
| Day -5 | Fludarabine 30 mg/m ² IV over 1 hour Treasulfan 14 g/m ² IV over 2 hours |
| Day -4 | Fludarabine 30 mg/m ² IV over 1 hour Treasulfan 14 g/m ² IV over 2 hours |
| Day -3 | Fludarabine 30 mg/m ² IV over 1 hour |
| Day -2 | Fludarabine 30 mg/m ² IV over 1 hour |
| Day -1 | TBI 200 cGy (or escalated to 300 cGy, 400 cGy, or 450 cGy per guidelines outlined in the statistical considerations Section 14) |
| Day 0 | UCB transplant |

* Fludarabine will be increased to 40 mg/m² daily days -6 to -2 in the event of excessive graft failures

1. Treosulfan administration.

a. For patients for patients whose body surface area (BSA) > 1.0 m², TREO will be administered intravenously at a dose of 14 g/m²/day over 120 minutes for three consecutive days (day -6 to -4). Doses of 14 g/m²/day for infants and smaller children with low BSA results in significantly higher treosulfan exposure (AUC); therefore, the following BSA-dependent dosing schema will be used for the treatment of infants and smaller children when their BSA is ≤ 1.0 m². For patients > 120% of ideal weight, BSA will be calculated using adjusted weight.

| Body surface area (m ²) | Treasulfan dose (g/m ²) |
|-------------------------------------|-------------------------------------|
| ≤ 0.5 | 10.0 |
| > 0.5 – 1.0 | 12.0 |
| > 1.0 | 14.0 |

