and completeness by the FHCRC study staff. Queries are sent to the collaborating investigators if CRFs are inaccurate or incomplete. The study is monitored under the FHCRC Monitoring Plan. The FHCRC Data and Safety Monitoring Plan details the full scope and extent of monitoring and provides for immediate action in the event of the discovery of major deviations.

D. Oversight and Review of Safety Monitoring

An annual review of the progress of the study with respect to the monitoring plan will be performed by a Data and Safety Monitoring Committee (DSMC). As part of the annual renewal process, the PI will submit an accounting of patient enrollment and outcomes defining the monitoring plan in sufficient detail as to permit verification of the report through chart audit. The IRB provides a final level of annual review. Approval by the DSMC is a necessary but not sufficient condition for final approval by the IRB. The IRB will review the same continuation application and materials that are reviewed by the DSMC, and make an independent assessment of the progress of the trial and determine whether the perceived risk-benefit ratio continues to be acceptable.

13. Records

Clinical Statistics maintains a patient database at FHCRC to allow storage and retrieval of patient data collected from a wide variety of sources. The investigator will ensure that data collected conform to all established guidelines for coding, collection, key entry and verification. Each patient is assigned a unique patient number to assure patient confidentiality. Patients will not be referred to by this number, by name, or by any other individual identifier in any publication or external presentation. The licensed medical records department, affiliated with the institution where the patient receives medical care, maintains all original inpatient and outpatient chart documents. Patient research files are kept in a locked room. They are maintained by the FHCRC data collection staff which is supervised by an A.R.T. Access is restricted to personnel authorized by the Division of Clinical Research.

14. Statistical Considerations

The goal of this study is to show that the probability of graft failure using TREO/FLU/TBI as a sufficient conditioning regimen is statistically significantly less than the fixed historical benchmark of 10%. In addition, we hope to show that probability of day-200 NRM is consistent with a true probability that does not exceed 25%.

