The original rule for escalation of FLU/TBI based on excess graft failure will not be in place in the modified protocol; however the stopping rule for day-200 NRM will be expanded to accommodate the increase in accrual. In particular, a true day-200 NRM of 25% will be considered excessive, and this assessment will be made separately for each treatment arm. The expanded stopping rules will be assessed after every 10th enrolled patient becomes eligible for evaluation. The current distribution of patients enrolled to the two different arms is 34 to Arm 1 and 40 to Arm 2. Given these totals, we expect fewer than a total of 80 patients on either arm by the time a total of 130 has been reached. Therefore, the expanded stopping rules for TRM will be assessed after the 40th and 50th patients have been enrolled to Arms 1 and 2, respectively. In particular, this rule would be triggered in a particular arm if any of the following occurs: 13

NRM events among the first 40 (or fewer) patients; 16 among the first 50 (or fewer) patients; 19 among the first 60 (or fewer) patients; 22 among the first 70 (or fewer) patients; 24 among the first 80 (or fewer) patients. If the true probability of NRM is 0.15, the probability of stopping after 50 or 70 patients is approximately .005 and .005, respectively. If the true probability of day-200 NRM is 0.40, the stopping probabilities are approximately .77 and .85, respectively (estimated from 5,000 simulations).

Secondary endpoints will be evaluated and include overall survival (with 65 patients in an arm, we can be 80% certain that estimated one-year survival is within at least 0.08 of the true one-year survival), non-relapse mortality, platelet engraftment, acute and chronic GVHD, relapse, progression-free survival, and clinically significant infections. Each of these will be treated as a time-to-event endpoint, and Kaplan-Meier and cumulative incidence estimates will be used to summarize each, as appropriate.

15. References

1. Kurtzberg, J., M. Laughlin, M.L. Graham, et al., Placental blood as a source of hematopoietic stem cells for transplantation into unrelated recipients. *N Engl J Med*, 1996. 335(3): 157-66.
2. Gluckman, E., V. Rocha, A. Boyer-Chammard, et al., Outcome of cord-blood transplantation from related and unrelated donors. Eurocord Transplant Group and the European Blood and Marrow Transplantation Group. *N Engl J Med*, 1997. 337(6): 373-81.

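### Section 14 withdraws the only rule tied to excess graft failure, a primary endpoint, and puts no monitoring count in its place, while Sections 2 and 8 still describe the withdrawn rule

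*Combined protocol and SAP*

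**What the plan says.** Section 3 lists graft failure/rejection, with secondary graft failure, as the first primary endpoint and day-200 NRM as the second. Section 14 opens with the aim for the first of these, a rate "statistically significantly less than the fixed historical benchmark of 10" per cent. It gives no alpha, no critical count, and no statement of whether the test is pooled or per arm.

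Section 14 then says: "The original rule for escalation of FLU/TBI based on excess graft failure will not be in place in the modified protocol". The same sentence continues that "the stopping rule for day-200 NRM will be expanded to accommodate the increase in accrual". The per-arm NRM boundary is 13/40, 16/50, 19/60, 22/70 and 24/80, with looks from the 40th patient in Arm 1 and the 50th in Arm 2. At that point 34 and 40 patients had been enrolled, of a planned 130.

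Other sections read differently:

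- Section 2 (Treosulfan in cord transplant) says escalation rules are established, and adds: "For each arm, a true probability of graft failure of 5% (or less) will be accepted without dose escalation".
- Section 8.A, citing Section 14, says "dose escalations will occur in either arm if sufficient evidence exists to suggest that the true probability of graft failure exceeds 5" per cent.
- The conditioning table in Section 8.A refers to Section 14 for the escalated TBI levels, and its footnote says: "Fludarabine will be increased to 40 mg/m² daily days -6 to -2 in the event of excessive graft failures".

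Section 12 provides for investigator review of each patient's course at least twice monthly, and for annual DSMC and IRB review.

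**The concern.** Graft failure is the hazard that the protocol itself singles out for this setting. Section 2 reports that "Minnesota experienced 4 graft failures in their first 21 RIC patients receiving BU/FLU", and 6 failures in 10 in another busulfan/fludarabine cord series. Yet in the current Section 14 no number of graft failures, in either arm, prompts a pause or a review. A reader of Section 8 would believe that such a rule exists and would look for it in Section 14, which says it is not in place.

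The patients at stake are the 130 − 74 = 56 still to be enrolled, including those in Arm 2, which is defined by high risk of graft failure. The NRM rule covers them only in part, because a patient whose graft fails and who is alive at day 200 is not an NRM event.

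**Working it through.** **Inputs.** From Section 14: benchmark 10% for graft failure; 25% as excessive NRM; the NRM boundary and looks; 34 + 40 = 74 enrolled; 130 planned; 65 per arm (the figure used there for survival precision). From Section 2: 5% as the acceptable graft-failure rate. Not in the documents, so assumed: an exact one-sided test at 0.05, with 0.025 and 0.10 as the range.

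**1. The plan's own figures.** I used an exact sequential binomial calculation with looks at 40, 50, 60 and 70.

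- At a true NRM of 0.15, the stopping probability is 0.0049 by 50 patients and 0.0052 by 70. This reproduces the stated .005 and .005.
- At 0.40 it is 0.924 and 0.968, not the stated .77 and .85. A true NRM of 0.35 gives 0.766 and 0.850. That is a separate matter and does not affect this point.

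**2. How the NRM boundary is built.** Its counts equal the smallest k with P(X ≥ k | n, 0.25) < 0.20:

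| n | k | P(X ≥ k) | P(X ≥ k−1) |
|---|---|---|---|
| 40 | 13 | 0.179 | 0.285 |
| 50 | 16 | 0.163 | 0.252 |
| 60 | 19 | 0.149 | 0.225 |
| 70 | 22 | 0.136 | 0.202 |
| 80 | 24 | 0.182 | 0.255 |

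**3. The same construction for graft failure.** The smallest k with P(X ≥ k | n, 0.10) < 0.20 is 7/40, 8/50, 9/60, 10/70 and 11/80. Chance that one arm crosses by 70 patients:

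| True graft-failure rate | Looks from 40 | Looks from 50 |
|---|---|---|
| 5% | 0.7% | 0.5% |
| 10% | 21% | 20% |
| 15% | 67% | 66% |
| 20% | 93% | 93% |

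**4. Can the NRM rule stand in?** No share of graft failures ending in non-relapse death is given. As an illustration, assume 15% background NRM, 20% graft failure, and a share f of failures adding to NRM, so that NRM = 15% + 20% × f. The NRM rule then stops an arm by 70 patients with these probabilities:

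- f = 0 (NRM 15%): 0.005
- f = 0.25 (NRM 20%): 0.06
- f = 0.5 (NRM 25%): 0.26
- f = 1 (NRM 35%): 0.85

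How far it substitutes depends almost entirely on f, which the documents do not supply.

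**5. When is the primary aim lost?** Success needs P(X ≤ c | n, 0.10) ≤ alpha; failure number c + 1 rules it out.

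- Pooled, n = 130: P(X ≤ 6) = 0.0207, P(X ≤ 7) = 0.0456, P(X ≤ 8) = 0.0881, P(X ≤ 9) = 0.152. The aim is lost at the 7th failure (alpha 0.025), 8th (0.05) or 9th (0.10).
- Per arm, n = 65: P(X ≤ 1) = 0.0087, P(X ≤ 2) = 0.0360, P(X ≤ 3) = 0.0996. It is lost at the 2nd, 3rd or 4th failure respectively.

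**6. The boundary in step 3 does not detect that loss.** Take a 60/70 split. Eight failures in 60 and nine in 70 cross nothing, yet make 17/130 = 13%. At a true 10%, the pooled aim (alpha 0.05) is lost with probability 0.95. Neither arm crosses with probability (1 − 0.179) × (1 − 0.199) = 0.66.

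**The case against.** The strongest reply is that the trial is not unsupervised. The investigator sees every course at least twice monthly, DSMC approval is needed for continuation, the IRB judges risk and benefit independently, and the NRM rule can stop either arm. That stands. A reader might infer that a failing arm would enrol to the end; the documents support only that it could, because none of these reviews has a stated graft-failure criterion.

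A reader might also infer that a safety stop was removed. The withdrawn rule is described as a trigger for escalation, not for stopping accrual or for futility. A hold on accrual would be new, and is a design recommendation. The demonstrable defect is the conflict between sections and the absence of any count.

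Nor do the documents show that the aim is already lost or that graft failure is high: they report no outcomes for the 74 enrolled. The 4/21 series used a different regimen, in patients the protocol itself describes as at risk for graft failure because of less prior treatment. Carrying its 19% over to both arms here is unsupported. The chance of eight or more failures among 74 is 0.03 at a true 5%, 0.46 at 10% and 0.99 at 20%.

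Finally, a boundary against 10% does not mark loss of the aim. Step 6 of the working confirms this, so the two need separate provisions.

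**Conclusion.** The point holds in this form: Section 14 leaves a primary endpoint without any pre-specified monitoring count for up to 56 further patients, and Sections 2 and 8 still describe the withdrawn rule. The conflict and the gap rest on the text alone. The size of the benefit rests on the assumed boundary: by 70 patients it would detect a true rate of 15% in about two arms in three, and 20% in about nine in ten. The count at which the aim is lost cannot be read from the plan. It is the 7th to 9th failure if pooled over 130, and the 2nd to 4th if tested in arms of 65, over one-sided alpha from 0.025 to 0.10. The sponsor should make the change; it is a gap in monitoring, not evidence that any patient has been harmed.

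**What to change.** 1. Reconcile Section 2, Section 8.A with its table and footnote, and Section 14, so that they agree on whether a graft-failure rule is in force. This review takes no position on which dosing rule is right.
2. Add to Section 14 a per-arm graft-failure boundary at the looks already planned (Arm 1 from 40, Arm 2 from 50): 7/40, 8/50, 9/60, 10/70, 11/80. Crossing it holds accrual to that arm pending DSMC review. State when a patient counts as evaluable for graft failure.
3. Separately state the alpha and sidedness, whether the test is pooled or per arm, and the count at which the aim is lost. Report that count to the DSMC when it is reached. It should inform the committee and not halt accrual automatically: at an acceptable true 5%, the 3rd failure in 65 still occurs with probability 0.64, and the 8th in 130 with probability 0.32.

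The cost is a paragraph in Section 14, corrections in two other sections, and one extra count at existing looks. The downside is the chance of an unnecessary pause: 0.7% per arm by 70 patients at a true 5%, rising to 21% at exactly 10%.

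### The stopping probabilities printed for a true day-200 NRM of 0.40 (.77 and .85) are those for 0.35; the stated boundaries give about .92 and .97 at 0.40

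*Combined protocol and SAP*

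**What the plan says.** Section 14 drops the earlier escalation rule for graft failure and keeps an expanded stopping rule for day-200 NRM. It sets the standard as follows: "a true day-200 NRM of 25% will be considered excessive, and this assessment will be made separately for each treatment arm". On timing it says: "The expanded stopping rules will be assessed after every 10th enrolled patient becomes eligible for evaluation". The first expanded look differs by arm, because the rules "will be assessed after the 40th and 50th patients have been enrolled to Arms 1 and 2, respectively".

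The boundaries are cumulative event counts per arm, and reaching any one of them is enough to stop. The limit at the 40-patient look is 13 events. The wording for the first two looks is: "NRM events among the first 40 (or fewer) patients; 16 among the first 50 (or fewer) patients". The limits for the three later looks follow in the same sentence: "19 among the first 60 (or fewer) patients; 22 among the first 70 (or fewer) patients; 24 among the first 80 (or fewer) patients".

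Two scenarios describe how the rule behaves, both from 5,000 simulations. At a true NRM of 0.15, the probability of stopping is about .005 at 50 patients and .005 at 70. For the high rate the text reads: "If the true probability of day-200 NRM is 0.40, the stopping probabilities are approximately .77 and .85, respectively". One set of figures is given for both arms, and none is given at 25%.

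**The concern.** A rule that stops at 13 events in 40 patients should stop very often when 16 events are expected in 40 (0.40 × 40). A stopping probability of only .77 after a second look at 50 patients is too low for that rate.

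This is the only numerical stopping boundary left in Section 14, and these two sentences are the only account of how it performs. Anyone using them to judge whether the rule gives enough protection is told that an arm with 40% NRM would escape stopping by 50 patients about 23% of the time. On the printed boundaries the figure is about 8%. If 0.35 was the intended upper scenario, the reader has instead been given the wrong rate and does not know what the rule was designed to detect.

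**Working it through.** **Inputs, all from Section 14.** Stop an arm if its cumulative NRM count reaches 13 of 40, 16 of 50, 19 of 60, 22 of 70 or 24 of 80. Looks fall every 10 patients, starting at 40 in Arm 1 and at 50 in Arm 2. True rates are 0.15 and 0.40.

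**Method.** Let X_n be the number of NRM events in the first n patients, binomial with rate p. At the first look the stopping probability is P(X_40 ≥ 13). At each later look, carry forward the distribution of the count among paths that have not yet stopped, add a Binomial(10, p) increment, and add the probability at or above the new boundary to the running total. This is exact, with no simulation error.

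**Step 1: reproduce the plan's figure at 0.15 (looks from 40).**
- First look: P(X_40 ≥ 13) = .0043. The look at 50 adds .0006, giving .0049 by 50.
- The looks at 60 and 70 add .0002 and .0001, giving .0052 by 70.
- The plan prints .005 and .005, so both agree. Single looks would give .0019 at 50 and .0004 at 70. The plan's figures are therefore cumulative, with looks starting at 40.

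**Step 2: the same calculation at 0.40.**
- First look: .8715. The look at 50 adds .0525, giving **.924** by 50 (printed .77).
- The looks at 60 and 70 add .0273 and .0162, giving **.968** by 70 (printed .85).
- Differences: .924 − .77 = .154 and .968 − .85 = .118.
- Monte Carlo standard error for 5,000 runs: √(.77 × .23 / 5000) = .006 and √(.85 × .15 / 5000) = .005. Noise cannot explain the gaps. A separate 200,000-run simulation gave .925 and .968.

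**Step 3: other readings of the rule at 0.40.**

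| Reading | By 50 | By 70 |
|---|---|---|
| Looks from 40, as stated | .924 | .968 |
| Looks from 50 | .905 | .963 |
| One look only, at 50 or at 70 | .905 | .945 |
| Must exceed the boundary, looks from 40 | .868 | .940 |
| Must exceed the boundary, looks from 50 | .844 | .934 |
| Boundaries raised by 2 | .790 | .899 |
| Given no stop at 40 | .409 | .747 |

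Monitoring after every patient gives the same result as the first row, and assumed earlier looks at 10, 20 and 30 only raise it. At 0.40 each stated boundary used alone already gives at least .87 (.872 at 40, .905 at 50, .928 at 60, .945 at 70). Extra looks can only add to that, so no choice of looks can bring the cumulative figure down to .77 or .85.

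**Step 4: which rate gives the printed figures (looks from 40)?**

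| True NRM | By 50 | By 70 |
|---|---|---|
| 0.34 | .720 | .808 |
| **0.35** | **.766** | **.850** |
| 0.36 | .807 | .885 |

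Only 0.35 matches both.

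**Step 5: figures by arm, by 50 / by 70 patients.**

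| True NRM | First look at 40 (Arm 1) | First look at 50 (Arm 2) |
|---|---|---|
| 0.15 | .005 / .005 | .002 / .002 |
| 0.25 | .22 / .26 | .16 / .21 |
| 0.35 | .77 / .85 | .72 / .83 |
| 0.40 | .92 / .97 | .90 / .96 |

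If an arm reached 80 patients, the 24/80 boundary would bring the 0.25 figures to .29 and .25. Section 14 expects fewer than 80 in either arm.

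**The case against.** The strongest reply is that nothing in the conduct of the trial changes. Monitoring acts on event counts, the boundaries are printed clearly, and the figures at 0.15 are right. At 0.40 the mistake understates the rule's sensitivity, so the real rule catches excess mortality more often than the text claims. All of this is correct. It limits the consequence but does not make the sentence true.

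Three narrower points also have force.

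- The Arm 2 figures depend on taking its stated first look at 50 at face value. The boundary list exempts no arm from the 13/40 limit, Arm 2 already had 40 patients enrolled, and the earlier NRM rule is not reproduced. If Arm 2 was also checked at 40, its figures equal Arm 1's.
- Leaving out a scenario at 25% is a gap in reporting, not an arithmetic error, and anyone can compute it from the boundaries.
- The documents do not show whether the rate or the probabilities were misprinted. That 0.35 was simulated is inferred from the match.

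Nor do the documents say that the DSMC or the IRB rely on these particular figures. Section 12.D says only that they review progress and the monitoring plan each year.

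**Conclusion.** The point holds. On the stated boundaries, the probability of stopping by 50 and by 70 patients at a true NRM of 0.40 is .92 and .97, not .77 and .85. The errors are about 15 and 12 percentage points, far beyond simulation noise. The printed pair is the result for 0.35.

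The calculation assumes independent patients with a common NRM rate, cumulative counts, and looks at 40, 50, 60 and 70. Reproducing the plan's own .005 and .005 supports that reading. With Arm 2's first look at 50, the values at 0.40 are .90 and .96, so the conclusion is the same in either arm.

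This is a wrong statement about how the stopping rule performs. It is not evidence that the rule is unsafe, and it should be corrected without touching the boundaries.

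A secondary point concerns 25%, the rate the plan calls excessive. There the rule stops an arm by 70 patients with probability of only about .21 to .26, and the plan does not show this.

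**What to change.** Rerun the simulation or the exact calculation, confirm which upper rate was intended, and correct the sentence in Section 14 in one of two ways:

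- change the true rate from 0.40 to 0.35 and keep .77 and .85; or
- keep 0.40 and print .92 and .97.

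Two additions are recommended. First, state whether Arm 2 is assessed at 40 patients; if it is not, give its own figures (.002 / .002 at 0.15, and .72 / .83 at 0.35 or .90 / .96 at 0.40). Second, give the stopping probability at 25% (.22 / .26 with looks from 40, .16 / .21 with looks from 50).

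The cost is one corrected sentence, one or two more if the additions are taken up, and a short calculation. Boundaries, accrual and patient management stay as they are.
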